2.3.2.4 Safety Follow-up

All subjects who complete the study and do not enter the OLE study, or who discontinue early, including those withdrawn from IMP, will have a SFU visit 20 weeks after their final dose of IMP, as applicable.

2.4 Determination of sample size

2.4.1 Power calculations for the primary endpoint

The sample size assumptions for BKZ versus placebo are based on the ACR50 response data from the Phase 2b BKZ study in subjects with moderate-to-severe PsA (PA0008). The median ACR50 responses of the top 3 dose groups (BKZ 160mg, 320mg, and 320mg [initial dose] plus 160mg) at Week 12 in the Tumor necrosis factor-naïve (TNF-naïve) population are conservatively assumed for the Week 16 endpoint. The observed median ACR50 response rate of the top 3 BKZ doses in the TNF-naïve population in study PA0008 was 43.8%.

The placebo ACR50 response at Week 16 is based on the TNF α -naïve population in PA0008 (6.1% at Week 12, subjects with available measurement (n)=33); Mease et al, 2015), FUTURE 2 study in the subgroup of TNF α -naïve subjects (15.9%, n=63; McInnes et al, 2015), FUTURE 3 study (11.8%, n=93; Nash and Mease, 2018), and FUTURE 5 study in a mixed tumor necrosis factor alpha (TNF α) exposure population (8.1% at Week 16, n=332; Mease et al, 2018). Therefore, the estimated ACR50 response at Week 16 in the placebo group is assumed to be 16%.

The sample size for showing statistical superiority of BKZ vs placebo was calculated using a 2-sided 2-sample Chi-square test with continuity correction (Fleiss et al, 1980). Assuming 420 subjects in the BKZ group and 280 subjects in the placebo group, the test for detecting statistical superiority of BKZ 160mg Q4W vs placebo based on ACR50 response at Week 16 has >99% power to detect a true treatment difference of 27.8% (odds ratio (OR) 4.09).

2.4.2 Power calculations for secondary endpoints

The assumptions for power calculations of the secondary endpoints included in the hierarchy, and for which supporting data exists, are based on the interim results of the Phase 2b BKZ study PA0008 and the FUTURE 1, FUTURE 2, FUTURE 5, and SPIRIT P1 studies. All power calculations for binary endpoints were performed using a 2-sided 2-sample Chi-square test with continuity correction (Fleiss et al, 1980). All power calculations for continuous endpoints were performed using a 2-sided 2-group Satterthwaite t-test (Moser et al, 1989).

For the PASI90 response at Week 16, the BKZ 160mg Q4W treatment response at Week 12 is 45% (n=20) in the TNF α -naïve population of PA0008 at Week 12 and 46% (n=28) at Week 12

in the mixed TNF α exposure population. The placebo PASI90 response at Week 16 is based on the subgroup analyses of TNF α therapy-naïve subjects in PA0008 (9.1% at Week 12; n=22), FUTURE 2 study (9.7% at Week 24; n=63), and SPIRIT P1 study (1.5% at Week 12; n=67). Therefore, a placebo PASI90 response rate of 10% is assumed. With those assumptions, the study has >99% power to detect a true treatment difference at an assumed 60% of subjects with BSA $\geq 3\%$ of the planned sample size.

For change from Baseline in HAQ-DI at Week 16, the between treatment differences of the change from Baseline in HAQ-DI of in the mixed TNF α exposure population of the PA0008 at Week 12 were used. The BKZ 160mg Q4W treatment group mean change from Baseline in HAQ-DI at Week 12 of -0.37, Standard deviation (SD)=0.47 (n=41) versus placebo mean change from Baseline in HAQ-DI at Week 12 of -0.13, SD=0.50 (n=42). With those assumptions, the study has >99% power to detect a true treatment difference of -0.24 at the planned sample size.

For change from Baseline in PCS of SF-36 at Week 16, the between treatment differences of the change from Baseline in PCS of SF-36 of the TNF α -naïve population of FUTURE 2 study (Kavanaugh et al, 2016) at Week 24 were used. The BKZ 160mg Q4W treatment group assumes the secukinumab 150mg treatment group mean change from Baseline in SF-36 PCS at Week 24 of 7.91, SD 7.38 (n=63) versus placebo mean change from Baseline in SF-36 PCS at Week 24 of 2.08, SD 9.51 (n=63). With those assumptions, the study has >99% power to detect a true treatment difference of 5.83 at the planned sample size.

For MDA at Week 16, the BKZ 160mg Q4W treatment response at Week 12 in PA0008 is 46.3% (N=41) in the mixed TNF α exposure population of PA0008. In the placebo group, 14.3% of subjects achieved MDA at Week 12 (n=42). With those assumptions, the study has >99% power to detect a true treatment difference of 32% (OR=5.17) at the planned sample size.

For change from Baseline in vdHmTSS at Week 16, the between treatment differences of the change from Baseline in vdHmTSS at Week 16 of the SPIRIT P1 study in a TNF α -naïve population (Mease et al, 2017) were used. The SPIRIT P1 study ixekizumab 80mg sc Q2W treatment group least square mean (LSM) change from Baseline at Week 16 0.06 and SD 0.720; and LSM change from Baseline 0.36 and SD 0.710 for placebo are assumed. With those assumptions, the study has a 95% power to detect a true treatment difference of -0.30, assuming 45% of subjects with elevated hs-CRP and/or bone erosion, in the planned sample size.

There is uncertainty in the final percentage of subjects with elevated hs-CRP and/or bone erosion at Baseline that will be recruited to the study and the variability in the subgroup. To demonstrate the sensitivity of the sample size calculation for this study, [Table 2-1](#) shows the power function for a fixed total sample size of 840 subjects in the Randomized Set (RS) population for this secondary efficacy analysis, varying the percentage of subjects with elevated hs-CRP and/or bone erosion at Baseline and the treatment difference and estimated standard deviation on the change from Baseline in vdHmTSS at Week 16.

Table 2-1: Treatment effect elevated hs-CRP and/or bone erosion at Baseline for secondary efficacy analyses

Subjects with elevated hs-CRP and/or bone erosion at Baseline	Treatment difference/standard deviation	
	Treatment effect = -0.3 SD = 0.72 vs. 0.71	Treatment effect = -0.35 SD = 0.81 vs. 0.93
20%	67	62
25%	76	72
30%	84	79
35%	89	85
40%	92	89
45%	95	92
50%	96	95

hs-CRP=high-sensitivity C-reactive protein ; SD=standard deviation

For dactylitis-free state at Week 16, dactylitis resolution data of the FUTURE 5 study (Mease et al, 2018) at Week 16 were used to estimate the BKZ 160mg Q4W treatment and placebo groups. The treatment effect estimate from the secukinumab 150mg treatment group at Week 16 of 56% (n=103) is assumed versus a placebo group estimate of 32% (n=124). With those assumptions and having 11% of subjects with Baseline dactylitis, the pooled PA0010/PA0011 studies have a 66% power to detect a true treatment difference of 24% (OR= 2.71).

For enthesis-free state at Week 16, enthesis resolution data from the FUTURE 5 study at Week 16 were used to estimate the BKZ 160mg Q4W treatment and placebo groups. In FUTURE 5 The treatment effect estimate from the secukinumab 150mg treatment group at Week 16 was 55% (n=141) and the placebo group estimate was 36% (n=192). Assuming a BKZ response of 55% and a placebo rate of 39% and having 25% of subjects with Baseline enthesis the pooled PA0010/PA0011 the studies have a 69% power to detect a true treatment difference of 16% (odds ratio 1.91). Treatment difference in change from Baseline in vdHmTSS at Week 16 in the overall population is estimated using the data from the FUTURE 5 study in a mixed TNF α exposure population. The BKZ 160mg Q4W group treatment difference compared to placebo is estimated to be the same as the difference in change from Baseline in vdHmTSS at Week 16 between the secukinumab 150mg group and placebo which is 0.42, assuming a SD of 1.13 for BKZ and SD=2.44 for placebo. With these assumptions the study has 76% power to detect a treatment difference of 0.42 in the planned sample size.

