4.5 Multiple comparisons/multiplicity

A step-down closed testing procedure will be applied for the primary endpoint and some secondary endpoints. The testing procedure will account for multiplicity and control the family-wise type I error rate at alpha=0.05 (2-sided).

For each test, on each binary efficacy endpoint, the null hypothesis is that the conditional odds ratio is equal to one ($H_0: OR_{T1T2} = 1$). The alternative hypothesis is that the conditional odds ratio is not equal to one ($H_A: OR_{T1T2} \neq 1$).

For each test, on each continuous efficacy endpoint, the null hypothesis is that there is no difference between treatment groups ($H_0: T_1 - T_2 = 0$). The alternative hypothesis is that there is a difference between treatment groups ($H_A: T_1 - T_2 \neq 0$).

T_1 refers to BKZ and T_2 to placebo.

According to this strategy, the statistical testing of an endpoint can be investigated only if the null hypothesis for the previous endpoint has been rejected (i.e., if $p < 0.05$). [Table 4-5](#) shows the testing order for these endpoints.

Table 4-5: Sequential testing procedure of primary/secondary efficacy endpoints (fixed sequence testing procedure) (All efficacy endpoints at Week 16)

BKZ 160mg Q4W	
H_1	ACR50 Response superior to Placebo
H_2	Change from Baseline HAQ-DI superior to Placebo

BKZ 160mg Q4W	
H ₃	PASI90 Response superior to Placebo
H ₄	Change from Baseline SF-36 PCS superior to Placebo
H ₅	MDA superior to Placebo
H ₆	Change from Baseline vdHmTSS* superior to Placebo on subjects with elevated hs-CRP and/or with at least one bone erosion (hs-CRP ≥ 6 mg/L and/or erosion-positive)
H ₇	Enthesitis-free state superior to Placebo (based on pooled PA0010 and PA0011 W16 data)
H ₈	Dactylitis-free state superior to Placebo (based on pooled PA0010 and PA0011 W16 data)
H ₉	Change from Baseline vdHmTSS** superior to Placebo

ACR=American College of Rheumatology; BKZ=bimekizumab; CfB=change from Baseline; H=hypothesis;

HAQ-DI=Health Assessment Questionnaire - Disability Index; hs-CRP=high sensitivity C-reactive protein;

LEI=Leeds Enthesitis Index; MDA=Minimal Disease Activity; PASI=Psoriasis Area and Severity Index.

PCS=Physical Component Summary; Q4W=every 4 weeks; SF-36=Short-Form 36-item Health Survey;

vdHmTSS=Van der Heijde modified Total Sharp Score.

* It is planned to enroll a minimum of 45% of subjects who are positive for elevated hs-CRP (hs-CRP ≥ 6 mg/L) and/or who have at least 1 bone erosion at Screening.

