- If the total score is missing at a post-Baseline visit (ie, only "N" or "S" is recorded for all joints) or if JSON or ES score is missing then the missing total score will be imputed using MI imputation.

For the change from Baseline analyses, subjects who withdraw early and have radiographs taken at their early withdrawal visit should be included in the analysis. In such cases, one or more imputation methods may be applied for the subjects with less than 2 radiographs. In addition to any such imputation approach that is selected, an analysis excluding subjects with less than 2 radiographs from the analysis should be performed.

In the testing hierarchy (Table 4-5), 2 endpoints are defined based on the vdHmTSS:

- Change at Week 16 from Baseline in vdHmTSS for subjects with elevated hs-CRP and/or with at least one bone erosion at Baseline (planned to be approximately 45% of the overall population). This is the 6th endpoint in the sequential testing hierarchy.
- Change at Week 16 from Baseline in vdHmTSS for all subjects. This is the 9th endpoint in the sequential testing hierarchy.

The 2 endpoints will be analyzed in the radiographic set.

At Week 16, imaging data collected outside ± 14 days of the expected visit date will be excluded from the analysis.

For the Week 24 interim analysis only, in the primary analysis of these 2 endpoints, missing data at Week 16 will be imputed based on value at Screening (as there is no value collected in between) using MI-MCMC / Monotone regression. Since VdHmTSS is only collected at Baseline prior to Week 16, only the second MI step to address monotone missing pattern and generating 100 imputations will be processed (Section 4.2.2.2).

8.2.1.6 Enthesitis-free state at Week 16 in the subgroup of subjects with enthesitis at Baseline

The Leeds Enthesitis Index (LEI) consists of 6 items, 3 for the right part and 3 for the left part of the body. The body parts are Lateral epicondyles of the humerus, Medial femoral condyle, and

Achilles tendons. Each item is scored for tenderness with either 1 or 0 (tenderness, no tenderness, respectively). The total score ranges from 0 (no enthesitis) to 6 (severe enthesitis).

Note that LEI is collected for all subjects regardless of their Baseline score.

In case 4 items are missing, the LEI will be set to missing. If at least 3 items are available, the available items will be assessed and scored and then weighted by the number of the assessed items (AI) as shown in the formula below:

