8.2.2 Primary analysis of secondary efficacy variables

The secondary efficacy variables will be analyzed for all subjects in the RS by treatment group (except for vdHmTSS for which the analysis will be performed on the RAS).

As indicated in [Table 4–5](#), there are 8 secondary endpoints included in the testing hierarchy that will be tested in a chronological order until one is failed to be statistically significant.

For the other secondary endpoints (secondary endpoints which are not part of the testing hierarchy), the p-values produced by the statistical models will be considered nominal since these endpoints are not controlled for multiplicity.

For the secondary composite and non-composite binary endpoints, the same estimand structure (composite estimand) as the one defined for the primary efficacy analysis of the primary efficacy endpoint ([Section 8.1.2](#)) will be used. The NRI approach for handling missing data and the same analysis model will be considered, and the analysis results will be presented similarly, with the exceptions that the analyses performed on pooled data from PA0010 and PA0011 subjects will consider the region and the study-id factor as possible covariates for the modelling.

The statistical hypothesis for the binary variables at Week 16 is that the conditional odds ratio in the BKZ group compared with placebo treatment group is equal to 1.

For the secondary continuous endpoints, the analysis will evaluate the hypothetical estimand as defined below:

- Population = Subjects enrolled according to the protocol-specified inclusion/exclusion criteria and randomized to IMP.
- Subject level outcome = variable as stated in [Section 2.2.1.2](#)
- IE handling = An IE is defined as discontinuation of study treatment prior to Week 16. A hypothetical strategy for addressing IE will be implemented. This estimand targets the treatment difference in a scenario where withdrawal from study treatment does not occur, such that outcomes for subjects without an IE are as observed, and outcomes for subjects with an IE are treated as though they had completed treatment through Week 16 but on Placebo. A MI strategy will be used to impute any missing data and observed data after IE which will be set to missing prior to running MI. Such data will be imputed using reference-based MI, in which the MI model is based on data from the Placebo group.

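### The 66% (H8) and 76% (H9) in section 2.4.2 are single-test powers; under the Table 4-5 fixed sequence neither hypothesis can exceed 66%, and independence would give about 43% and 33%

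*SAP*

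**What the plan says.** SAP section 2.4.2 introduces its figures as power for the secondary endpoints included in the hierarchy. It names the methods: a two-sided chi-square test with continuity correction for binary endpoints and a two-sided Satterthwaite t-test for continuous ones. For the last four hypotheses it states:

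- H6, vdHmTSS in subjects with elevated hs-CRP and/or bone erosion: "With those assumptions, the study has a 95% power to detect a true treatment difference of -0.30".
- H7, enthesitis-free state, pooled PA0010/PA0011: 69%.
- H8, dactylitis-free state, pooled: "the pooled PA0010/PA0011 studies have a 66% power to detect a true treatment difference of 24" percentage points.
- H9, vdHmTSS in the overall population: "With these assumptions the study has 76% power to detect a treatment difference of 0.42 in the planned sample size".

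The primary endpoint (section 2.4.1) and H2 to H5 are each given more than 99%.

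Section 4.5 sets a fixed sequence that is meant to "control the family-wise type I error rate at alpha=0.05 (2-sided"). Under it, "the statistical testing of an endpoint can be investigated only if the null hypothesis for the previous endpoint has been rejected". Section 8.2.2 repeats that the secondary endpoints are "tested in a chronological order until one is failed to be statistically significant". Section 8.2.1.5 places the two vdHmTSS endpoints: for the subgroup, "This is the 6th endpoint in the sequential testing hierarchy"; for all subjects, "This is the 9th endpoint in the sequential testing hierarchy".

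The SAP does not label the powers as marginal, reports no power under the sequence, and gives no correlations between endpoints.

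**The concern.** Section 2.4.2 speaks of what the study has, for endpoints it describes as members of the hierarchy. A reader will take 76% as the chance that the overall-population radiographic result is established, and 66% as the same for dactylitis. Under section 4.5 those chances are joint probabilities: H8 needs H6, H7 and H8 all to be rejected, and H9 needs H6 to H9. The figure printed for H9 is also higher than the figure for the gate directly in front of it.

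What is at stake is how a missing claim is read. Someone relying on 76% would find an unestablished H9 surprising and might count it against the treatment. On the plan's own marginal assumptions it may well be the more likely outcome, mainly because H7 and H8 have modest power.

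**Working it through.** **Step 1: reproduce the stated powers as single tests.**

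*H9.* Inputs (sections 2.4.1 and 2.4.2): 420 BKZ, 280 placebo, difference 0.42, SD 1.13 and 2.44.
- SE = √(1.13²/420 + 2.44²/280) = √(0.00304 + 0.02126) = 0.1559
- Noncentrality = 0.42/0.1559 = 2.69, Satterthwaite df about 360
- Power 76.6% (stated 76%)

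*H6.* Inputs: 45% of each arm, so 0.45 × 420 = 189 and 0.45 × 280 = 126; difference 0.30; SD 0.72 and 0.71.
- SE = √(0.72²/189 + 0.71²/126) = 0.0821
- Noncentrality = 0.30/0.0821 = 3.65
- Power 95.4% (stated 95%)

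*H7 and H8.* These depend on the size of PA0011, which the SAP does not give. Assuming PA0011 adds 240/120 to 280/140 subjects (BKZ/placebo), the continuity-corrected powers are 67% to 70% for H7 and 65% to 68% for H8. The stated 69% and 66% fit an addition of about 260/130, so they are accepted.

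*H1 to H5.* All compute to above 99.9%, so these gates cost almost nothing. Even at 0.99 each, the independence figures in step 3 would fall only to 41.1% for H8 and 31.3% for H9.

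**Step 2: what holds under any dependence.** A joint probability cannot exceed its smallest component.
- H8: at most min(0.95, 0.69, 0.66) = 66%
- H9: at most min(0.95, 0.69, 0.66, 0.76) = 66%
- Lower bounds: H8 0.95 + 0.69 + 0.66 − 2 = 30%; H9 0.95 + 0.69 + 0.66 + 0.76 − 3 = 6%

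**Step 3: independence, with H1 to H5 taken as 1.**
- H7: 0.95 × 0.69 = 65.6%
- H8: 0.95 × 0.69 × 0.66 = 43.3%
- H9: 0.95 × 0.69 × 0.66 × 0.76 = 32.9%

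**Step 4: positive correlation (assumed).** Joint probability from a multivariate normal with the stated powers as margins:

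| Common correlation | H8 | H9 |
|---|---|---|
| 0 | 43.3% | 32.9% |
| 0.1 | 45.0% | 35.7% |
| 0.3 | 48.5% | 41.2% |
| 0.5 | 52.0% | 46.7% |
| 0.7 | 55.9% | 52.5% |
| 0.9 | 60.9% | 59.8% |

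A more structured set (H6/H9 0.45 to 0.9, H7/H8 0 to 0.4, other pairs 0 to 0.2) gives H8 43% to 49% and H9 34% to 42%.

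**Step 5: the H6/H9 overlap.** The H6 subgroup is nested in the H9 population. With the SAP's SDs, the covariance of the two differences is 0.72²/420 + 0.71²/280 = 0.00303, so their correlation is about 0.00303/(0.0821 × 0.1559) = 0.24. This matters little: even at 0.45 to 0.9, with all other pairs at zero, H9 rises only to 33.7% to 34.6%, because H6 is already at 95%. The loss comes from H7 and H8.

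**The case against.** The best defence is that nothing printed is wrong. The figures reproduce, section 2.4.2 names single two-sample tests as their basis, and power to detect a given difference is ordinary per-test language. Reporting marginal power for a hierarchy is common, and sections 2.4.2 and 4.5 do not contradict each other. This stands as far as it goes: a reader might infer that 66% and 76% are miscalculated, and they are not.

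A second objection also stands. A reader might infer that the design simply delivers 43% for H8 and 33% for H9. Those values need independent tests, which the SAP does not assume and which is untenable for at least H6 and H9. Nor do the planning inputs form one joint model. H6 and H9 come from different external studies; a difference of 0.30 in the 45% subgroup and 0.42 overall would imply (0.42 − 0.45 × 0.30)/0.55 = 0.52 in the lower-risk remainder.

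Third, the harm is partly contained. Section 8.3.2.3 provides a Week 16 vdHmTSS comparison with a confidence interval and nominal p-value whatever happens in the sequence. Sections 8.2.1.6 and 8.2.1.7 repeat the enthesitis and dactylitis analyses in PA0010 alone, and section 8.2.2 puts the results for all hierarchy endpoints in one overview table.

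None of this removes the central point. For endpoints introduced by their place in the hierarchy, the chance of a confirmatory result is the relevant quantity. It is missing, and for H9 it is lower than the printed figure by at least 76 − 66 = 10 points.

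**Conclusion.** The point holds as a gap in reporting, not as an arithmetic error. The powers for H6 to H9 are correct for each test alone. They are not the powers of a design that tests these hypotheses in a fixed sequence.

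The 66% ceiling on H8 and H9 needs no correlation assumption, only the SAP's stated powers. The rest is conditional. With H1 to H5 at about 100%, independence gives about 66% (H7), 43% (H8) and 33% (H9); common correlations from 0 to 0.5 give about 43% to 52% for H8 and 33% to 47% for H9.

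It is tempting to add that both endpoints are more likely to fail or go untested than to succeed. The documents do not support that for H8, which passes one half at a common correlation of 0.5. For H9 it holds up to 0.5 but not at 0.7, where the figure is 52.5%.

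**What to change.** In section 2.4.2, label the H6 to H9 figures as marginal, single-test powers at two-sided 0.05, and keep them, including the 76%. Beside them give the power under the Table 4-5 sequence:

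- the independence values (H7 about 66%, H8 about 43%, H9 about 33%);
- a range over stated correlation assumptions, for example H8 43% to 52% and H9 33% to 47% for common correlations of 0 to 0.5;
- the 66% ceiling for H8 and H9.

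The sequential values should not be entered as single fixed numbers without their assumptions. The cost is a few lines of SAP text and less favourable figures for H7 to H9. No test, alpha allocation, dataset or patient changes.

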3 DATA ANALYSIS CONSIDERATIONS

3.1 General presentation of summaries and analyses

Statistical analysis and generation of TFLs and statistical outputs will be performed using SAS[®] Version 9.3 or higher unless otherwise specified. All tables and listings will use Courier New font size 9.

Descriptive statistics will be displayed to provide an overview of the study results.

For categorical parameters, the number and percentage of subjects in each category will be presented. Unless otherwise noted, the denominator for percentages will be based on the number of subjects included in the respective analysis set. Subjects with missing data can generally be accounted for using one of the 2 following approaches:

- Percentages will be summarized based on all subjects in the analysis set and a “Missing” category (corresponding to subjects with missing data for the variable being summarized) will be included as the last row in the list of categories being summarized. This approach will be used when reporting demography, Baseline characteristics, some NAb tables and some shift tables from Baseline for laboratory data.
- Percentages will be based only on those subjects with observed data for the variable being summarized. As the denominator may be different from the number of subjects in the analysis set being considered, the denominator should be displayed in the table. The general format for displaying this will be “n/Nsub (%”).

Unless otherwise noted, all percentages will be displayed to 1 decimal place. No percentage will be displayed for zero counts, and no decimal will be presented when the percentage is 100%.

For continuous parameters, descriptive statistics will include number of subjects with available measurements (n), arithmetic mean, standard deviation (SD), median, minimum, and maximum (unless otherwise stated).

For hs-CRP variable, the summary statistics should contain arithmetic mean, geometric mean, geometric coefficient of variation (CV), median, first and third quartile (Q1 and Q3), minimum and maximum (for the value and the ratio to Baseline). The geometric CV (%) will be calculated using the following formula:

$$CV = \sqrt{e^{SD_{ln}^2} - 1}$$

Where SD_{ln} represents the SD of the ln-transformed hs-CRP value.

For BKZ PK concentrations, geometric mean, geometric CV, 95% confidence intervals (CIs) for geometric mean (assuming log-normally distributed data) will be calculated if at least $\frac{2}{3}$ of the values of interest are above the lower limit of quantification (LLOQ). If this is not the case, only median, minimum, and maximum will be presented.

Decimal places for descriptive statistics will always apply the following rules:

- “n” will be an integer
- Mean, SD, SE, and median (Q1 and Q3 when applicable) will use 1 additional decimal place compared to the original data (for a derived score, number of decimals of the original data considered is the one obtained where deriving the score in the absence of missing data)
- CV (%) will be presented with 1 decimal place
- Minimum and maximum will have the same number of decimal places as the original value.

If the number of decimal places reported in the original data is varied then either the maximum raw number of reported decimal places or 3 will be used, whichever is the lowest, as a guide for the descriptive statistics.

The table below provides the number of decimals to be reported for each continuous efficacy endpoint:

Table 3-1: List of decimals for continuous efficacy endpoints

Continuous efficacy endpoint	Decimal place used for minimum and maximum	Decimal places used for Mean, SD (or SE) and median
BASDAI	1	2
DAPSA	1	2
DAS28[CRP]	2	3
EQ-5D-3L dimension scores	0	1
EQ-5D-3L (VAS)	0	1
FACIT-Fatigue subscale score	1	2
HAQ-DI	3	4
hs-CRP	2	3
LDI	1	2
LEI	1	2
mNAPSI	0	1
PASDAS	1	2
PASI	1	2
PGA-Arthritis /PhGA-Arthritis	0	1
PGA-PsA / PhGA-PsA	0	1
PsAID-12	1	2
PsAQoL	1	2
PsARC	1	2
PtAAP	0	1
SF-36	2	3
SPARCC	1	2
TJC / SJC	1	2
vdHmTSS, Erosion score Joint space narrowing score	1	2
WPAI-SHP	1	2

BASDAI=Bath Ankylosing Spondylitis Disease Activity Index; DAPSA=disease activity index for psoriatic arthritis; DAS28[CRP]=disease activity score-28 based on C-reactive protein; EQ-5D-3L=Euro-Quality of Life 5-Dimensions 3 Level version; FACIT-Fatigue=Functional assessment of chronic illness therapy - Fatigue; HAQ-DI=Health assessment questionnaire – Disability index; hs-CRP=High sensitivity C-reactive protein; LDI=Leeds Dactylitis Index; LEI=Leeds Enthesitis Index; mNAPSI=Modified Nail Psoriasis Severity Index; PASDAS=Psoriatic Arthritis Disease Activity Score; PASI=Psoriasis Area and Severity Index; PGA-Arthritis=Patient's global assessment of Arthritis; PGA-PsA=Patient's Global assessment of Psoriatic Arthritis; PhGA-Arthritis=Physician's global assessment of Arthritis; PhGA-PsA=Physician's Global assessment of Psoriatic Arthritis; PHQ-9=Patient Health Questionnaire-9; PSAID-12=Psoriatic Arthritis impact of disease-12; PsAQoL=Psoriatic Arthritis Quality of Life; PsARC=Psoriatic Arthritis Response Criteria; PtAAP=Patient's assessment of Arthritis Pain; SF-36=Short-Form 36-item Health Survey; SJC=Swollen Joint Count; SPARCC=Spondyloarthritis Research Consortium of Canada ; TJC=Tender Joint Count; vdHmTSS=Van der Heijde modified Total Sharp Score; WPAI-SHP=work productivity and activity impairment questionnaire – specific health problem

Unless stated otherwise, continuous endpoints will be expressed as a change from Baseline which will be calculated as the value at a specific timepoint minus the value at Baseline.

Unless stated otherwise, statistical tests of efficacy variables will be presented as 2-sided p-values rounded to 3 decimal places. P-values less than 0.001 will be presented as “<0.001” and p-values greater than 0.999 will be presented as “>0.999.” Statistical comparisons will be performed by 2-sided statistical tests at the 0.05 level of significance. Least square means (LSM), OR and corresponding CI will be presented using 3 decimals.

UCB uses SAS in a 64-bit Windows environment, and it is well-documented that in this environment the maximum accuracy of any numeric value is 15 significant digits. However, SAS by default does not limit the accuracy of numeric values to 15 significant digits which, in certain instances, may result in inaccurate representation of the data and cause errors when used in subsequent calculations, particularly when comparing a value to a chosen threshold. This, in turn, could potentially result in a change in classification of a subject from a responder to a non-responder (and vice versa) if these values occur on a threshold used in the evaluation of response (or a critical laboratory value for example).

Therefore, in order to avoid issues caused by inaccurate floating point representation of numeric values, temporary variables are created (ie, for absolute values, change and percentage change from Baseline) during programming which are rounded to 12 decimal places prior to comparison to a specific threshold in the derivation of a response parameter. This does not imply inherent rounding on the analysis variables for absolute value, change or percentage of change which are retained unrounded in the final analysis dataset. Thus, rounding is applied exclusively during the derivation of new response parameters or critical value variables, and the rounded values are created on a temporary basis only.

The SAS® outputs supportive of any inferential statistics that are part of the hierarchical testing procedure (ie, all inferential statistics associated with the endpoints in [Table 4-5](#)) will be provided as a separate PDF document in addition to TFLs. These outputs will be included in the ‘Documentation of Statistical Methods’ section of the clinical study report

Unless specified differently in this SAP, the order of treatment groups presented in tables from left to right will be:

- Placebo
- Bimekizumab 160mg Q4W

- Adalimumab 40mg Q2W.

Selected tables may also include columns for all subjects (regardless of study treatment) and/or all subjects on BKZ (regardless of whether they shifted from placebo after the DBP or not).

The abbreviation for bimekizumab is BKZ, and ADA for adalimumab and will be used in table and listing headers. No abbreviation will be used for Placebo.

In the TFLs, subjects randomized to BKZ 160mg Q4W will be labeled as “BKZ 160mg Q4W”, subjects randomized to ADA 40mg Q2W will be labeled as “ADA 40mg Q2W” and subjects randomized to Placebo will be labeled as “Placebo / BKZ 160mg Q4W” (or “Placebo” when the TFLs report data from the DBP only).

For the ATP, all subjects on BKZ 160mg Q4W (that includes the subjects switching from Placebo at Week 16) will be labeled as “BKZ 160mg Q4W Total” in the TFLs.

Per protocol, visit windows of ± 2 days from the first dose at all visits through Week 16 and ± 3 days after Week 16 are permissible. For the SFU visit, the visit should occur no more than 3 days prior to the scheduled visit date and within 7 days after the scheduled visit date.

For the medical imaging collection date (at Week 16 and 52), the allowed visit window will be extended to ± 14 days around the scheduled visit date.

All by-visit tables will contain nominal (ie scheduled) visits only. Unscheduled visits will not be mapped to scheduled visits except for some assessments that may occur within the above visit window of a scheduled visit. In that case, the assessment will be mapped to the corresponding scheduled visit and will be used for the analysis unless data are present for that scheduled visit. Only data collected/mapped at the scheduled visits will be included in the analysis. The only deviation may concern unscheduled vendor data collected ([Section 10.5](#)).

Assessments collected at unscheduled and repeated visits will only be listed, except in the case of determining treatment-emergent markedly abnormal criteria for laboratory and vital sign parameters where all post-Baseline (scheduled and unscheduled) values will be used.

For by-visit tables summarizing efficacy data, the SFU visit will not be included but SFU efficacy data will be listed. By-visit tables summarizing safety data will however include the SFU visit. For PK, immunological and immunogenicity analyses, SFU data will be part of the data reported in some tables ([Section 9](#)).

A complete set of data listings containing all documented data and all derived data (eg, change from Baseline) will be generated.

Unless otherwise stated, listings will be sorted by treatment group, subject number within each treatment group (not randomization number), variable (if applicable) and visit (if applicable, including timing relative to dosing if applicable). For listings including non-randomized subjects, the non-randomized subjects will be shown first in the listing, ordered by subject number. All listings will include repeated and unscheduled measurements. Such measurements will appear in chronological order together with the scheduled visits (ie: a repeated measurement will appear directly after the visit and time relative to dosing for which the repeat measurement was performed). In all the listings dates will be presented in the format ‘YYYY-MM-DD’ and times will be presented in 24h clock format as ‘hh:mm’.

